11. PROCEDURES FOR EFFICACY EVALUATIONS

11.1. AK Lesions

11.1.1. AK Lesion Count

At the Screening and Day 1 Pre-Dose Visits, the selected Treatment Field must include 4-8 discrete qualifying AK lesion and no disqualifying lesions (Section 11.1.3).

At the Day 1 Pre-Dose Visit, all AK lesions in the selected contiguous 25 cm² Treatment Field will be identified, counted, and recorded. The approximate outline of each AK lesion will be transcribed on the Treatment Field Map on Day 1. A photograph of the subject's Treatment Field will be taken and a copy given to the Subject to assist the subject in locating their Treatment Field.

At visits after Day 1 specified below, the investigator will be given the Day 1 Treatment Map and Photograph of the Treatment Field for reference and asked to count the number of AK lesions identified within the Treatment Field.

If new AK lesions appear in the Treatment Field after Day 1, they **will** be counted.

If the subject has a LSR that prevents the investigator or designee from performing the AK count at a visit, the investigator or designee should document in the source document and CRF that the AK count was not obtained due to LSR local effects.

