5.2. Actinic Keratosis and Current Approaches to Treatment

Actinic keratosis (AK) is one of the most common dermatologic diagnoses and affects an estimated 58 million people in the United States. Estimated treatment costs in 2004 were \$1.2 billion (Warino 2006). AK is generally present as rough patches or papules with erythema and scaling on sun-exposed skin, predominantly in older individuals with fair skin (Fitzpatrick skin types I-III). The lesions are often asymptomatic, but they may itch or be tender to the touch. Histologically, AK is characterized by keratinocyte atypia in the deeper epidermis, with defective maturation of the superficial epidermis (Cohen, 2010). The most common reason for treatment is to prevent cutaneous squamous cell carcinoma (cSCC). Although the risk of progression to invasive SCC for a specific lesion may be low, it is widely regarded that 60% to 97% of SCCs originate from AK's (Hurwitz 1995, Mittelbronn, 1998). This estimate is supported by considerable genetic analysis that demonstrates shared chromosomal abnormalities and progressive changes in gene expression between AK and SCC (Kanjilal, 1995, Ortonne, 2002, Kanellou, 2008, Padilla, 2010). Consequently, AK is often referred to as cSCC *in situ* (Heaphy, 2000, Opiel, 2004, Röwert-Huber, 2007) and is part of the continuum of transformation from normal skin to AK and cSCC (Ziegler, 1994, Stockfleth, 2013).

Since AK results from malignant processes in sun-exposed skin (mainly face, scalp, and extremities), it is often necessary to treat entire fields and not only the individual lesions. Cryosurgery and laser-based therapies are less effective for this indication. Currently the most common topical drugs and treatments for field-treatments of AK are 5-fluorouracil (5FU), imiquimod cream, ingenol mebutate gel, photodynamic therapy (PDT), and diclofenac sodium in hyaluronic acid (Chetty, 2015).

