- The differences between the VDA-1102 10% treatment group and the placebo treatment group on the 4 exploratory efficacy endpoints consistently favored VDA-1102 10% across all 3 analysis populations. These differences (ITT population) were statistically significantly different (versus placebo) for change from baseline in the number of lesions with a grade ≥ 2 ($P = 0.03$) and change from baseline in the adjusted number of lesions weighted by grade ($P = 0.02$).
- There were no statistically or clinically relevant differences on any exploratory endpoint between the VDA-1102 5% and placebo treatment groups.
- Post-hoc analysis of an efficacy subset of patients who were only treated for AK Treatment Field lesions on the face (ie, not scalp) and represented approximately 75% of enrolled patients demonstrated that the VDA-1102 10% treatment group (ITT population) had a statistically significant greater reduction in the number of AK lesions compared to the placebo treatment group ($P = 0.02$).

- The positive finding for VDA-1102 10% treatment group in the efficacy subset of patients with AK Treatment Fields only on the face was supported by similar treatment effect differences versus the placebo treatment group on the exploratory endpoints evaluated in the originally planned exploratory analyses.
- A post-hoc analysis of treatment group differences (ITT population) for progression of AK to Grade 3 indicated 2 subjects in the placebo treatment group progressed to grade 3 versus no subjects in the 2 VDA-1102 treatment groups.
- The inability to detect plasma concentrations of VDA-1102 or jasmonic acid using sensitive methodology in the subjects included in the PK sub-cohort suggests no systemic absorption of 200 mg VDA-1102 when applied once-daily topically for up to 28 days in a 25 cm² Treatment Field.

Further details of the results of this trial are provided in the VDA-1102 Investigator's brochure.

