11.1.2. Definition of AK Lesion Clearance

A prior AK lesion that is no longer seen **OR** no longer palpable is to be considered cleared and will not be counted, **even if a residual color or skin texture change remains in the skin.**

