12.9. General Restrictions

12.9.1. Medication and Other Therapeutic Restrictions

Prohibited Products and Procedures

All prescription medications, vitamins, medicinal products, and AK therapies (including chemical peels and photodynamic therapy) are prohibited from Day 1 through the subject's exit from the study unless explicitly permitted below or approved in writing by the Investigator and Study Medical Monitor.

Topical creams, lotions, makeup, or gels of any kind are prohibited within the selected Treatment Field and the 3-inch area around the border of this field from Day 1 through the subject's exit from the study unless prescribed by the site Investigator and documented in the subject's file.

Permitted Products and Procedures

Allowed medications or therapies during the study must be documented and include:

- Daily medications: Subjects taking vitamins, prescription medications, or medical products daily may continue taking those products as long as the subject has been taking them continually for at least 2 months prior to Screening with no significant change in dose or dosing interval. These medicinal products must be recorded on the appropriate Concomitant Medication pages. All other prescription medications, medicinal products, and vitamins (with exceptions noted in the bullets below) are prohibited without prior approval of the Investigator and the Medical Monitor.
- Non-prescription prn medications: The following non-prescription medications are allowed without prior consultation: ≤ 1500 mg acetaminophen, ≤ 1650 mg naproxen, or ≤ 1200 mg ibuprofen within a 24-hour period for not more than 2 consecutive days.
- Prescription prn medications: Prescribed medications taken prn including antihistamines, bronchodilators, sleep medications, and intranasal, inhaled, and ophthalmic corticosteroids that are listed as concomitant medications at Screening and/or Day 1 Pre-Dose Visits are permitted. PRN medication taken daily are to be considered "daily medications."
- Physical treatments or procedures such as cryo-destruction, surgical excision, curettage, dermabrasion, or laser resurfacing more than 3 inches from the border of the Treatment Field are permitted.
- Topical creams, lotions, makeup, or gels applied outside the 3-inch border area of the selected Treatment Field is permissible. Subjects, however, should not change such products between and screening and their exit from the trial.

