14. CONCOMITANT MEDICATION

Any prescription or non-prescription medication, alternative medication, herbal product, homeopathic substance, etc. that the subject receives while they are enrolled in the trial or that was taken within 2 months of Screening will be referred to as a Concomitant Medication. The Investigator is to record the use of all concomitant medications, both prescribed and over-the-counter, in the subject medical record.

Subjects should be advised against taking any new medication, both prescribed and over-the-counter, without consulting the Investigator, unless the new medication is urgently required for emergency use. Subjects taking medication other than those listed as prohibited in Section 12.9.1 may continue taking their routine medications and vitamins so long as they have been taking them for at least 2 months prior to Screening with no change in dose or dosing interval.

At Screening and Day 1 Pre-Dose Visits, the study site personnel will review each subject's concomitant medications to ensure that subjects are not taking any prohibited medications listed in Section 12.9.1.

The Investigator and his designees are obligated to ensure the well-being of all subjects during this study. Consequently, no medication or treatment should be withheld from a subject requiring medical intervention. This may include treatments received by the subject prior to enrollment as well as in response to any new medical conditions that developed during the study. The Investigator (or designee) must inform a subject when concomitant medical intervention or treatment is indicated and report this in the appropriate section of the CRF.

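### The clearance definition ignores cause, so a Treatment Field lesion removed or cleared by something other than study drug can be scored as cleared

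*Combined protocol and SAP*

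**What the plan says.** Section 11.1.1 gives the counting rule. With the Day 1 map and photograph to hand, the investigator is "asked to count the number of AK lesions identified within the Treatment Field". New lesions are included. The only special case is a local skin reaction that hides the field, when the site documents that "the AK count was not obtained due to LSR local effects".

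Section 11.1.2 defines clearance. A prior lesion that is out of sight, or "no longer palpable is to be considered cleared and will not be counted", even if some colour or texture change remains. Either condition is enough, and nothing is said about cause.

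Section 12.9.1 prohibits AK therapies from Day 1 to study exit. It permits excision, cryo-destruction, curettage and similar procedures only more than 3 inches from the field border. The prohibition applies "unless explicitly permitted below or approved in writing by the Investigator and Study Medical Monitor". Section 14 adds that "no medication or treatment should be withheld from a subject requiring medical intervention".

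Section 17.7.2 keeps in the mITT population every enrolled and dosed subject who did not fail Exclusion Criterion #2, and runs all efficacy analyses on it. Section 17.7.3 removes violations and major deviations from the Per Protocol population, and under Section 17.8 the sponsor decides which events those are. Sections 17.2 and 17.6 leave analysis details and missing-data handling to a SAP whose text is not in the supplied documents.

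**The concern.** The primary endpoint is meant to show what the ointment does. A definition that looks only at whether a lesion is present at Week 16 gives the same score to a lesion cleared by study drug and one cut out or frozen at Week 10. If it was the last lesion in the field, the subject becomes a complete-clearance responder because of the other treatment.

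The error runs one way: taking a lesion away can only lower the count. The study is open-label with no control arm, so each cohort's rate is read on its own and nothing offsets the bias. Section 5.6.4 says the results will inform Phase 3 design and dose selection. The two secondary measures, at least 75% clearance and change in lesion number, rest on the same count.

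**Working it through.** **Can the event reach the primary analysis?**

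1. In-field treatment is restricted but possible, through the written-approval exception in 12.9.1 or the welfare clause in Section 14.
2. The subject can still be counted at Week 16. Section 7.5 encourages subjects who stop study drug to stay for the remaining assessments.
3. Under 11.1.2 a lesion fully excised or successfully frozen is no longer seen, so it is cleared and not counted.
4. The subject remains in mITT (17.7.2).
5. The result is an observed count, possibly zero. It is not a missing value, so a missing-data rule would not reach it.

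**Plan figures.** 40 (Part A) + 40 (Part B) + 70 (Part C) = 150. Per cohort, 40 + 70/2 = 75. At least 70 with data implies a loss of up to 5/75 = 6.7%. These reproduce. The plan has no formal sample size calculation to test.

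**Effect on complete clearance.** If m subjects are scored as responders only because a lesion was removed or otherwise treated, the rate is too high by m/n:

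- n = 75: m = 1, 1.33 points; m = 3, 4.00 points; m = 5, 6.67 points.
- n = 70: m = 1, 1.43 points; m = 3, 4.29 points; m = 5, 7.14 points.
- Facial subset, assuming about 75% facial as in Phase 2a: 0.75 × 75 ≈ 56, so 1/56 = 1.8 points per affected facial subject.

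The table shows the rate and 95% Clopper-Pearson interval (the method in 17.3.1) after m subjects are rescored as not cleared, at n = 75. The starting rates and m are assumptions, because the documents give neither.

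| m rescored | Start 15/75 | Start 30/75 |
|---|---|---|
| 0 | 20.0% (11.6–30.8) | 40.0% (28.9–52.0) |
| 1 | 18.7% (10.6–29.3) | 38.7% (27.6–50.6) |
| 3 | 16.0% (8.6–26.3) | 36.0% (25.2–47.9) |
| 5 | 13.3% (6.6–23.2) | 33.3% (22.9–45.2) |

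A subject contributes to m only if all other field lesions (4 to 8 at baseline, plus any new ones) have also gone.

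**Effect on partial clearance.** This endpoint does not need every other lesion to clear. With 4 lesions at baseline and 2 left, clearance is 2/4 = 50%. Removing one gives 3/4 = 75%, and the subject becomes a partial responder. With 8 at baseline and 3 left, 5/8 = 62.5% becomes 6/8 = 75%.

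**The case against.** The strongest reply is that the plan already makes the event exceptional. In-field AK therapy is prohibited, procedures are kept more than 3 inches away, and Exclusion Criterion 10 turns away subjects unwilling to avoid other therapy to the field. All of that stands. It makes the event uncommon but does not say how to score it.

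Second, the Per Protocol analysis may catch it. Section 17.8 counts as major any deviation that even possibly has a significant effect on data quality, and unapproved removal of an endpoint lesion fits. Treatment approved in writing might not count as a deviation, however, and mITT keeps the subject either way.

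Third, affected subjects may be traceable. Table 1 lists numbering of lesions at the efficacy visits, the Day 1 map outlines each lesion, and Section 14 requires interventions to be reported in the CRF. It would therefore be too strong to say that they cannot be identified. What is missing is any link from those records to the score.

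Fourth, the SAP might contain a rule. If so, the analysis side is answered, but sites count under the protocol's definition and the two would have to agree.

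A reader might go further and infer that disease progression in general is reported as clearance, since Section 5.2 says AK "is part of the continuum of transformation from normal skin to AK and cSCC". The text does not support that. Grades serve eligibility only (11.1.3), so an untreated lesion that thickens to Grade 3 is still an AK and still counted. A partially biopsied lesion that remains visible and palpable is also still counted. A lesion re-diagnosed as malignant may remain visible and palpable too; whether it leaves the AK count is not settled.

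Nor does Phase 2a supply a frequency. Its report that "2 subjects in the placebo treatment group progressed to grade 3 versus no subjects in the 2 VDA-1102 treatment groups" concerns Grade 3 progression, not removal or re-diagnosis. It shows none on active drug, and this trial has no placebo arm.

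**Conclusion.** The point holds in a narrow form. Section 11.1.2 is an operative rule without a condition on cause. On its wording, a Treatment Field lesion removed or destroyed by a procedure, or cleared by a non-study AK therapy, can be scored as cleared in the mITT primary and secondary endpoints. No section states outright that treated lesions are cleared; this follows from an unqualified definition and the absence of any exception.

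The size is 1.3 points per affected subject at n = 75, or 1.4 at n = 70, on complete clearance, given that all other lesions have cleared. The number of such subjects is unknown and probably small, and zero is possible. Three in one cohort would shift its rate by 4.0 to 4.3 points, well inside the width of the planned interval. Unlike sampling error, though, the shift has a fixed direction.

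**What to change.** Add to Sections 11.1.1/11.1.2 and 17.3.1/17.3.2, and mirror in the SAP:

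> A Treatment Field lesion that after Day 1 is removed or destroyed by a procedure, is treated with a non-study AK therapy, or is diagnosed as malignant is counted as present (not cleared) from that visit on, and the subject is not a complete-clearance responder at Week 16.

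State alongside it that permitted bland moisturizer, treatment of local skin reactions and a partial biopsy do not trigger the rule. Without that carve-out, measures the protocol already foresees would turn genuine drug clearance into failure. Naming malignancy in the rule also settles the open question about re-diagnosed lesions.

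Record the event and its date on the lesion-count CRF page, and report the number of affected subjects by cohort.

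The cost is one sentence with its carve-out and one CRF item. The clearance rate may be slightly lower, because some treated lesions might have cleared on study drug by Week 16 and the rule scores them as failures. This is a scoring rule only and leaves decisions about treating a subject unchanged.

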11.1.2. Definition of AK Lesion Clearance

A prior AK lesion that is no longer seen **OR** no longer palpable is to be considered cleared and will not be counted, **even if a residual color or skin texture change remains in the skin.**

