Study Design 
This Phase 2 clinical trial is a 3-part, open-label, multi-center study involving a non-occluded, daily topical dermal application of 1 of 2 strengths of VDA-1102 ointment for approximately 12 weeks (84 days) to an initial 2 cohorts of subjects. The first 40 eligible subjects will be enrolled into Cohort 1 (Part A). Cohort 1 subjects will be assigned to receive approximately 200 mg of 10% VDA-1102 twice-daily (BID). Once approximately 40 subjects have been enrolled in Cohort 1, Cohort 1 will be closed to enrollment and Cohort 2 (Part B) will be opened for enrollment. Cohort 2 subjects will be assigned to receive approximately 200 mg of 20% VDA-1102 once-daily (QD). Once approximately 40 subjects have been enrolled in Cohort 2, an additional 70 subjects will be randomly assigned to Cohort 1 or Cohort 2 (Part C) in a 1:1 ratio.
 
To qualify for the study, subjects aged 18 (inclusive) or older must have signed informed consent and met the study enrollment criteria that include having 4-8 actinic keratosis (AK) lesions within an approximate 25 cm² area on the cheek, forehead, or hairless scalp (the "Treatment Field").
	

Parts A, B, and C of this clinical trial will each include the same 3 study periods, a Screening Period (Day -21 through Day 1 Pre-Dose), a Treatment Period (Day 1 Dosing through Week 12), and a Post-Treatment Follow-Up Period (Week 13 through Week 16).

During the **Screening Visit** (up to 21 days pre-dose) subjects who have given written informed consent will undergo safety assessments, Treatment Field identification, and other qualifying procedures.

At the **Day 1 Pre-Dose Visit**, eligible subjects will return to the investigative site for baseline assessments as well as final eligibility screening. Subjects who continue to meet the enrollment criteria will be enrolled and will continue to the Day 1 Dosing Visit. The number of AK lesions within the Treatment Field will be recorded.

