5.6. Rationale for Study Design and Subject Population

5.6.1. Efficacy

VDA-1102 has shown relevant pharmacological effects *in vivo* in the UVB-induced SKH-1 hairless mice model of actinic keratosis and skin cancer. In this pre-clinical study, dermal application of VDA-1102 led to a significant ($p < 0.0001$) reduction in the number of lesions relative to vehicle, that was comparable to the reduction noted with the comparative control compound ingenol mebutate (Picato®) 0.05%. Clinical effects were observed within 1–2 weeks of treatment initiation, although full clinical benefit was observed after 3-4 weeks.

In the Phase 2a study (Section 5.5.2, above) subjects treated once-daily with 10% VDA-1102 or placebo for 4 weeks (28 days) had a modest reduction from baseline in the total number of AK lesions (32.1% versus 27.8%, respectively). The decrement in the number of lesions of subjects in the per protocol population who had Treatment Fields located on their face (not scalp) was more impressive and statistically significantly (median 50%; mean $41.3\% \pm 38.5\%$ for the VDA-1102 10% treatment group versus median 10%; mean $29.4\% \pm 32.5\%$, for the placebo treatment group, $P = 0.022$ adjusted for age, gender and site).

In the small (N=5) completed Cohort 1 of the Phase 1B trial summarized in Section 5.5.3, subjects treated with 10% VDA-1102 twice-daily for 8 weeks had a 74% reduction in the number of AK lesions in their Treatment Field. Aside from 2 subjects with reversible skin reactions, the drug was well-tolerated and safe. Together, these data suggest VDA-1102 has therapeutic effects and further evaluation of the dosing regimen/dose and longer duration of treatment is warranted.

In contrast to the aforementioned Phase 2a study where 200 mg of 10% VDA-1102 ointment was applied once-daily for 4 weeks and the completed Cohort 1 of the small ongoing Phase 1b study where 200 mg of 10% VDA-1102 ointment was applied twice-daily for 8 weeks, the dosing frequency in Part A (Cohort 1) of the current clinical trial remains 200 mg of 10% VDA-1102 ointment twice-daily; however, the treatment duration will be extended to 12 weeks.

In Part B (Cohort 2) of the current trial, the strength of the VDA-1102 ointment increases from 10% to 20% but the dosing frequency drops from twice-daily to once-daily. The treatment duration will be the same as in Part A, 12 weeks.

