7.3. Study Assessments

The Table of Assessments appears below. The number preceding the √ denotes the number of times this procedure will be performed at that visit (e.g. 3√ means 3 times). If the √ is not preceded by a number, then the procedure will be performed only once.

Table 1: Schedule of Study Assessments

ASSESSMENTS	STUDY PERIODS, STUDY VISITS, AND STUDY DAYS							
	SCREENING PERIOD		TREATMENT PERIOD				POST-TREATMENT FOLLOW-UP PERIOD	
	Screening Visit	Day 1 Visits		Week 4 Visit	Week 8 Visit	Week 12 / Early Termination Visit ¹	Week 13 Visit	Week 16 Visit
	Day -21 to Day -1	Day 1 Pre-Dose	Day 1 Dosing	Day 29 ±4	Day 57 ±5	Day 85 ±5	Day 92 ±5	Day 113 ±5
Informed Consent	√							
Enrollment criteria and safety data review	√	√						
Demographics & Medical History	√							
Adverse events recording	√	√		√	√	√	√	√
Concomitant medications recording	√ ²	√		√	√	√	√	√
Vital signs	√	√		√	√	√		√

¹ Subjects attending an Early Termination Visit (Section 7.5) will undergo Week 12 Visit procedures. In addition, women will undergo a Urine Pregnancy Test.

² Prior concomitant medications will be recorded at Screening, which includes all ongoing medications and medicinal products or with a stop date within **2 months** preceding Screening. All topical skin treatments (i.e., medicinal or physical) received in the **4 months** prior to Screening will be recorded.

ASSESSMENTS	STUDY PERIODS, STUDY VISITS, AND STUDY DAYS							
	SCREENING PERIOD		TREATMENT PERIOD				POST-TREATMENT FOLLOW-UP PERIOD	
	Screening Visit	Day 1 Visits		Week 4 Visit	Week 8 Visit	Week 12 / Early Termination Visit ¹	Week 13 Visit	Week 16 Visit
	Day -21 to Day -1	Day 1 Pre-Dose	Day 1 Dosing	Day 29 ±4	Day 57 ±5	Day 85 ±5	Day 92 ±5	Day 113 ±5
Physical examination		√		√	√	√		√
Height / Weight	√							
12-Lead ECG ³	√	√				√	√	√
Clinical laboratory testing ^{3, 4}	√	√				√	√	√
Treatment Field Selection	√	√						
AK lesions numbering, counting and grading	√	√		√	√	√	√	√
Local Skin Reaction Score		√		√	√	√	√	√
Treatment Field photograph, Template, and Map prepared		√						
Urine Pregnancy Test (UPT) ⁵	√	√				(√ ⁶)	√	

³ Clinical laboratory testing and 12-lead ECG will only be performed at Week 13 and/or Week 16 Visits if the results from the previous visit were abnormal and clinically significant.

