11.1.3. AK Lesion Eligibility

To be eligible for this trial, the Treatment Field must contain **4-8 AK lesions** that meet each of the following criteria:

- a. Grade 1 or 2 AK lesions only - not Grade 3; The definitions of AK Grades to be used for eligibility purposes are as follows:
 - Grade 1 – mild (slightly palpable AK that are felt better than seen)
 - Grade 2 – moderate (moderately thick AK that are easily seen and felt)
 - Grade 3 - severe (very thick, obvious, and/or hyperkeratotic AK). Treatment Fields selected for this trial must **not** contain any Grade 3 AK lesions.
- b. located on the subject's head including the face or balding scalp but not on the lips, ears, submandibular area, or neck;
- c. located in an area of the subject's head that easily visible to the subject in a mirror;
- d. discrete (i.e., no borders that are clearly touching one another);
- e. a maximum diameter 10 mm (inclusive) in any direction; and

- f. not atrophic, pigmented, or Bowenoid.

AK lesions grades will not be recorded in the CRF since the AK lesion grades are not an endpoint in this study.

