12.6.3. Post-Treatment Follow-Up Period

✓ ***Week 12 through Week 13 Visit***

- No procedures will be performed on these days.

✓ ***Week 13 Visit***

Note: *Despite the overlap between the windows for the Week 12 and Week 13 Visits, the Week 13 Visit should occur at least 5 days after the Week 12 Visit.*

On Day 92 (±5 days) the following procedures will be performed on all subjects:

- Adverse event(s) will be recorded

- Concomitant medications documented
- Urine Pregnancy Test will be performed on all women and results recorded.
- Local Skin Reaction Score in the Treatment Field
- AK lesion in the Treatment Field: count (11.1.1)
- Trial instruction review including an appointment for the next visit will be given.

✓ ***Week 14 through Week 16 Visit***

- Site personnel will communicate with the subjects on Week 15 (Section 12.7) to review the trial instructions and to remind each subject of their next site visit. Subjects will be reminded to bring all unreturned study drug with them to the next visit.

✓ ***Week 16 Visit***

On Day 113 (± 5) the following procedures will be performed on all subjects:

- Adverse event(s) will be recorded
- Concomitant medications documented
- Vital signs: peripheral blood pressure, respiratory and heart rates, and oral temperature will be recorded
- Physical examination
- Local Skin Reaction Score in the Treatment Field
- AK Lesion in the Treatment Field: count (11.1.1)

Subjects will be thanked for their participation in the trial and exit the study.

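### The clearance rule in Section 11.1.2 drops an AK that can still be felt once it is no longer seen, so clearance rates can only be equal to or higher than under a rule that keeps palpable AKs; the size is unknown and may be zero

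*Combined protocol and SAP*

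**What the plan says.** Section 11.1.2 defines clearance of a prior lesion: "A prior AK lesion that is no longer seen OR no longer palpable is to be considered cleared and will not be counted". The word OR is in bold capitals. The sentence goes on to say that leftover colour or texture change does not prevent clearance.

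Section 11.1.3 defines Grade 1 as "slightly palpable AK that are felt better than seen" and Grade 2 as lesions that are both easily seen and easily felt. Both grades may enter, so every qualifying lesion is palpable at baseline. The grade definitions are given for use at entry.

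The Week 16 efficacy endpoints in Section 8 (complete clearance, ≥75% clearance, change in count) all rest on this count. Section 11.1.1 adds new lesions to it. Section 17.3.1 reports the primary endpoint as a proportion per cohort with a Clopper-Pearson interval. There is no control arm (Synopsis, Efficacy Analyses) and no blinding (Section 12.1.1). Section 5.6.4 says the results will inform Phase 3 design and dose selection.

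On recording, Section 11.1.3 says: "AK lesions grades will not be recorded in the CRF since the AK lesion grades are not an endpoint in this study". Table 1 in Section 7.3 lists "AK lesions numbering, counting and grading". In Section 12.6.3 the Week 13 entry reads "AK lesion in the Treatment Field: count (11.1.1", and the Week 16 entry likewise asks only for a count.

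**The concern.** For a Grade 1 lesion, touch is the better detector by the protocol's own description. Yet loss of the weaker sign, visibility, is enough to score the lesion cleared. A lesion could therefore be counted as cleared while an assessor can still feel it as an AK.

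The main output is an absolute rate per cohort. A definition that admits more lesions as cleared shifts that rate, and the confidence interval does not show the shift because it covers sampling error only. With no concurrent control and no blinded reading, nothing in the design would reveal or offset it. A Phase 3 plan built on these rates would carry the shift forward.

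The other route, visible but no longer palpable, is not treated as an error here.

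**Working it through.** The plan gives no figure on this point, so there is none to reproduce. The check has two parts: the direction, which can be proved, and the size, which can only be illustrated.

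**Direction.** Each prior lesion is in one of four states.

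| Seen | Palpable | Cleared under 11.1.2 | Cleared if palpable AKs are kept | Cleared only if neither sign remains |
|---|---|---|---|---|
| no | no | yes | yes | yes |
| no | yes | **yes** | **no** | **no** |
| yes | no | yes | yes | no |
| yes | yes | no | no | no |

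Any rule that never clears a palpable AK clears a subset of what 11.1.2 clears. New lesions add the same number under every rule. So, for the same lesion states, 11.1.2 can never give a higher count or lose a complete or ≥75% response. Enumerating every combination for 4 to 8 lesions, with 0 or 1 new lesion, against both comparators gives (4⁴+4⁵+4⁶+4⁷+4⁸) × 2 × 2 = 87,296 × 4 = 349,184 comparisons, with 0 exceptions.

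**Size, illustration only.** All inputs are assumed:
- 6 lesions per field (entry allows 4 to 8).
- c = chance that a lesion is no longer palpable as an AK at Week 16: 30%, 50% or 74%. The ends lie near two net count reductions in Section 5.6.1: 32.1% on 10% VDA-1102 in Phase 2a, and 74% in 5 Phase 1b subjects. These are not per-lesion clearance rates. The text available does not give the clearance rule behind them; if it was the same OR rule, they already include the effect.
- u = chance that a still-palpable AK is judged unseen: 0.1 to 0.2, with no source.
- Within-subject correlation (ICC): 0 to 0.5, in steps of 0.01.

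Let J be the number of the 6 lesions no longer palpable. J is binomial(6, c) at ICC = 0, otherwise beta-binomial with a = c(1/ICC − 1) and b = (1 − c)(1/ICC − 1). Each remaining lesion is scored cleared with probability u. Then:
- complete clearance = E[u^(6−J)];
- ≥75% clearance = probability that at least 5 of 6 are scored cleared (5/6 = 83.3%, 4/6 = 66.7%);
- rise in count reduction = (1 − c)u.

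Worked case, c = 0.74, ICC = 0: complete clearance is 0.74⁶ = 16.4% at u = 0. At u = 0.2 it is (0.74 + 0.26 × 0.2)⁶ = 0.792⁶ = 24.7%, a rise of 8.3 points.

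| c | Rise in complete clearance (points) | Rise in ≥75% clearance (points) | Rise in count reduction (points) |
|---|---|---|---|
| 30% | 0.2 to 1.9 | 1.7 to 5.7 | 7.0 to 14.0 |
| 50% | 1.2 to 3.8 | 2.3 to 12.4 | 5.0 to 10.0 |
| 74% | 1.5 to 8.3 | 1.9 to 12.5 | 2.6 to 5.2 |

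At u = 0 every rise is 0. New lesions are not modelled; they would lower all rates.

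For scale, 12 of 75 (16.0%) has a Clopper-Pearson 95% interval of 8.6% to 26.3%. Its upper arm, 10.3 points, exceeds the largest complete-clearance rise shown.

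**Effect of changing the rule part-way.** The Synopsis enrols in sequence: "Cohort 1 will be closed to enrollment and Cohort 2 (Part B) will be opened for enrollment". If the rule changed after Part A, Cohort 1 would hold 40 subjects under the current rule and 35 under the new one, and Cohort 2 would hold 75 under the new one. Two equal regimens would then differ in complete clearance by 40/75 of the rise. The maxima are 40/75 × 1.9 = 1.0, 40/75 × 3.8 = 2.0 and 40/75 × 8.3 = 4.4 points.

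**The case against.** **The comparator is the reviewer's choice.** A looser rule always gives equal or higher clearance than a stricter one. The emphasised OR looks deliberate, no section contradicts it, and the grade definitions are for entry, not follow-up. This stands: the documents do not set the stricter rule for follow-up, and the point is a weakness of definition rather than an internal contradiction.

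**Grade 1 lesions are not said to be invisible.** A reader might infer that many already satisfy the clearance rule at baseline. The wording does not support that: a lesion felt better than it is seen may still be seen. Assessors also have the Day 1 map and photograph to help locate prior lesions. This stands as a limit on size.

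**The texture clause may already cover the case.** Texture can be felt, so some palpable residue is expressly allowed. This stands in part. The clause does not say where residual texture ends and a persisting AK begins, and the OR operates without it.

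**The effect cannot be recovered from the data.** A reader might infer this too, but no CRF is among the documents. What can be said is that no section available provides for recording the two signs separately, and that grades are kept out of the CRF.

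**The illustration has no documentary basis.** True. Nothing in the documents sources u, and the values of c are only loosely anchored.

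**Conclusion.** The concern holds in a limited form. Read literally, 11.1.2 scores an unseen but still palpable AK as cleared, and no section available requires both signs to be gone. The equal-or-higher direction follows from set inclusion and needs no assumption beyond the same observed lesion states. The size cannot be obtained from the documents and may be zero; the tabulated ranges rest wholly on assumed values.

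Two stronger conclusions are tempting and unsupported. One is that the reported rates will be materially inflated: nothing shows how often lesions end palpable but unseen. The other is that the rule distorts the comparison of regimens: it is the same in both cohorts, and nothing shows that it favours either. What is at issue is the absolute level of each cohort's rate. The change is worth making because it is cheap and the design offers no other check on that level.

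**What to change.** **If enrolment has not begun,** amend 11.1.2 along these lines: a prior lesion still palpable as an AK is not cleared, whether or not it is visible; residual colour or texture change that is not a palpable AK does not prevent clearance. Apply it at every post-baseline visit in both cohorts, and use assessor training to say which palpable residue still counts as an AK, since the wording alone leaves that to judgement.

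**If enrolment has begun,** keep the current rule as primary for all subjects, so that sequential enrolment does not mix definitions between cohorts.

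**In either case,** record seen (yes/no) and palpable (yes/no) for each mapped lesion, and report clearance under both rules as a sensitivity analysis.

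Cost: one sentence and a line of training, two CRF fields per lesion, and a second tabulation. Reported rates would be equal or slightly lower under the stricter rule. After a mid-trial start, earlier visits could be reported only under the current rule. If the Phase 2a and 1b trials used the OR rule, which the text available does not show, changing the primary rule would lose some comparability with them unless both rules are reported.

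Separately, and with no effect on clearance, clarify the grading entry in Table 1 against Section 11.1.3, which keeps grades out of the CRF, and Section 12.6.3, which asks only for a count.
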